7.1.1 Molecular pre-screening

Not applicable.

7.1.2 Screening

Written informed consent must be obtained before any study specific medical procedures are performed. All screening/baseline assessments (with the exception of Bone Marrow Aspirates) should occur within 21 days before Week 1 Day 1.

The screening visit window for bone marrow assessments is 56 days prior to Week 1 Day 1. Should bone marrow assessments have been performed before the main informed consent is signed but within 56 days of Week 1 Day 1, no further bone marrow sampling will be required at screening. At end of treatment, a bone marrow exploratory aspirate and/or biopsy must be collected even if the screening/baseline bone marrow exploratory aspirate and/or biopsy samples were not collected. During the screening visit, inclusion and exclusion criteria will be assessed. Screening assessments to confirm eligibility must be performed prior to randomization. The results of the real time quantitative polymerase chain reaction (RQ-PCR) and the bone marrow aspirate must be available prior to randomization and first dose of study treatment.

For details of assessments required during screening please refer to [Table 7-1](#).

Laboratory baseline assessments (including hematology, chemistry, coagulation and serum pregnancy test), physical examination including extramedullary involvement, performance status, ECG, height, weight and vital signs, evaluation of all relevant medical history including cardiovascular risk factors, CML disease history, including prior TKI therapy and antineoplastic medication and prior and concomitant medication must be performed prior to the first dose of study treatment. Patients with potassium, and/or magnesium and/or total calcium levels that are < LLN at screening, must have their potassium, and/or magnesium, and/or calcium replenished through supplementation and the levels must be within normal limits prior to the first dose of study drug.

A patient who has a laboratory test (peripheral blood test) results that do not satisfy the entrance criteria may have the tests repeated. These tests may be repeated as soon as the investigator believes the re-test results are likely to be within the acceptable range to satisfy the entrance criteria, but should be completed within approximately 2 weeks of the original screening visit date. In this case, the subject will not be required to sign another Informed Consent Form (ICF), and the original patient ID number assigned by the investigator will be used. In the event that the laboratory tests cannot be performed within the screening visit window, or the re-tests do not meet the entrance criteria, or other eligibility criteria have changed and are not met anymore, the patient is considered a screen failure, and must be discontinued from the study.

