7.2.2.5 Laboratory evaluations

Central laboratory will be used for analysis of hematology, biochemistry, coagulation, serum pregnancy and hepatitis marker specimens collected (safety monitoring). Details on the collections, shipment of the samples and reporting of results by the central laboratory are provided to investigators in the [CABL001A2301 Laboratory Manual]. The time windows granted for laboratory evaluations are identical with the corresponding visit time windows for each visit (see Section 7.1.5).

Table 7-4 Central clinical laboratory parameters collection plan

Test Category	Test Name	Frequency
Hematology	Hemoglobin, Platelets, Red blood cells, White blood cells, WBC Morphology with Differential (Basophils, Eosinophils, Lymphocytes, Monocytes, Neutrophils, Promyelocytes, Myelocytes, Metamyelocytes, Blast and Other)	Screening/Baseline, week 1 Day 1, week 2 Day 1, every 2 weeks from week 4 up to week 16, every 4 weeks up to week 96, and every 12 weeks thereafter, EOT and as clinically indicated
Chemistry	Hemoglobin A1c	Screening/Baseline, Week 12 and as clinically indicated
Chemistry	Albumin, Alkaline phosphatase, ALT (SGPT), AST (SGOT), Total Calcium, Creatinine, Creatinine kinase, Potassium, Magnesium, Sodium, Phosphorus, Direct Bilirubin, Indirect Bilirubin, Total Bilirubin, Total Cholesterol, LDL, HDL, Total Protein, Triglycerides, Blood Urea or Nitrogen (BUN), Uric Acid, Amylase, Lipase, Glucose (fasting)	Screening/Baseline, week 1 Day 1, week 2 Day 1, every 2 weeks from week 4 up to week 16, every 4 weeks up to week 96, and every 12 weeks thereafter, EOT, and as clinically indicated
Coagulation	International normalized ratio (INR)	
Hepatitis markers	HbsAg, HbcAb /anti-Hbc	Screening/Baseline
Serum Pregnancy test (if applicable)	Serum β -HCG testing	Screening/Baseline, every 4 weeks up to week 96, and every 12 weeks thereafter, EOT, unscheduled

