7.2.2.5.3 Pregnancy and assessments of fertility

[figure not shown]
All women of childbearing potential have to complete a serum pregnancy test at the screening visit, at every monthly visit until end of treatment visit. Pregnancy testing is not required for patients who are determined to be post-menopausal. The time windows granted for pregnancy testing are identical with the corresponding visit time windows for each visit. Refer to Table 7-1 of the Visit evaluation schedule. Serum pregnancy test will be performed by a central laboratory.

After Week 96 monthly urine pregnancy test must be performed by all women of childbearing potential between the three monthly visits (beginning at Week 100). Urine pregnancy tests may be performed at the investigational site or at home. Test results performed at home should be recorded onto a patient diary and brought to each scheduled visit for the site to review. If a test result indicates a pregnancy, the patient must contact the investigator immediately.

All pregnancies (including female partners of male patients) should be recorded on a Clinical Trial Pregnancy Form and reported by the investigator to the Oncology Novartis Drug Safety and Epidemiology Department (DS&E).

During the whole study, women of childbearing potential should employ the use of highly effective contraception. Highly effective contraception methods are defined in Section 5.3.

Sexually active males must use a condom during intercourse while taking the drug and for at least 3 days after stopping treatment and should not father a child in this period. A condom is required to be used also by vasectomized men in order to prevent delivery of the drug via seminal fluid.

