An extensive toxicology safety evaluation program (subchronic, chronic, reproductive toxicology, phototoxicity and genotoxicity studies) was conducted.

Safety pharmacology studies indicate that asciminib is not expected to cause effects on the vital functions of the CNS, and the respiratory systems. The IC₅₀ for asciminib in the hERG patch clamp is 11.4 μ M (4498 ng/mL). No cardiovascular effects were observed in a single dose jacketed telemetry study in dogs at doses up to 600 mg/kg or the invasive telemetry cardiovascular safety study up to 60 mg/kg. Furthermore, no changes in cardiovascular parameters related to QTc prolongation were observed using standard electrocardiography in the 4-week dog toxicity study and in cynomolgus monkey toxicity studies (up to 39 weeks of treatment).

Asciminib does not show mutagenic, clastogenic, or aneugenic potential in the *in vitro* assays or the MNT assessment *in vivo*; therefore, no potential risk for human is perceived.

As determined by the results of the phototoxicity assessment (*in vitro* and *in vivo*), phototoxic potential was identified in the mouse UV-LLNA assay. Given these data, patients should be advised to avoid prolonged exposure to sunlight (sunbathing), to avoid sunbed and to use sunscreen.

Toxicity studies performed in rats, dogs and cynomolgus monkeys (up to 26, 4 and 39 weeks of treatment, respectively) identified the pancreas, liver, hematopoietic system, adrenal and gastro-intestinal tract as potential target tissues.

Fetal malformations and increased visceral and skeletal variants were observed in the rat embryo-fetal development study. There was no evidence of effects on reproductive function in the fertility study; however there was a slight effect on male sperm motility and/or sperm count in individual animals. Phototoxic potential was identified in the phototoxicity (*in vitro* and *in vivo*) assessment.

Please refer to the latest [\[Asciminib Investigator's Brochure\]](#) for more details.

Non-clinical pharmacokinetics and metabolism

The preclinical pharmacokinetic profile of asciminib has been investigated in three species: mouse, rat and dog. In these species, asciminib exhibited low to moderate clearance, a moderate volume of distribution and a short apparent terminal half-life. Bioavailability was found to be low in rodents and moderate to high in dog.

Asciminib displayed high plasma protein binding across all tested species (2-6% free fraction).

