Coagulation	D	7.2.2.5.2	X	X	X	X		X		X		X	X	X	X	X	X	X	X	X	X	

Visit name	Category	Protocol Section 7	Screening Phase	Treatment Phase																	
				Screening/ Baseline (Day -21 to -1)	Week 1 Day 1	Week 2 Day 1	Week 4	Week 6	Week 8	Week 10	Week 12	Week 14	Week 16	Week 20	Week 24	Week 28	Week 32	Week 36	Week 40	Week 44	Week 48
Serum Pregnancy test (if applicable)	D	7.2.2.5.3	X			X		X		X		X	X	X	X	X	X	X	X	X	X
Hepatitis markers	D	7.2.2.5.2	X																		
Liver assessments	D			as clinically indicated																	
Efficacy assessments		7.2.1																			
Blood collection for BCR-ABL1 quantification by RQ-PCR	D	7.2.1.1	X			X		X		X		X		X				X			X
Blood collection for exploratory BCR-ABL1 mutation analysis by Sanger Sequencing	D	7.2.1.1		X																	

Visit name	Category	Protocol Section 7	Screening Phase	Treatment Phase																		
				Screening/ Baseline (Day - 21 to -1)	Week 1 Day 1	Week 2 Day 1	Week 4	Week 6	Week 8	Week 10	Week 12	Week 14	Week 16	Week 20	Week 24	Week 28	Week 32	Week 36	Week 40	Week 44	Week 48	Week 52
Exploratory BCR-ABL1 mutation analysis (Sanger Sequencing) for patients with mutations at Week 1 Day 1	D	7.2.1.1									X					X			X			X
Bone Marrow Aspirate/Cytogenetics -scheduled	D	7.2.1.2	X (Screening window - 56 days)													X						X
Cardiac Assessments		7.2.2.6																				
ECG	D	7.2.2.6.1	X	X	X	X					X					X						
Cardiovascular risk factor assessments (including Family History)	D	7.2.2.6.2	X																			
Echocardiogram	D	7.2.2.6.3	X												X							
Pulmonary Function Test	D	7.2.2.6.4	X												X							

	Category	Protocol Section 7	Screening Phase	Treatment Phase																		
Visit name			Screening/ Baseline (Day -21 to -1)	Week 1 Day 1	Week 2 Day 1	Week 4	Week 6	Week 8	Week 10	Week 12	Week 14	Week 16	Week 20	Week 24	Week 28	Week 32	Week 36	Week 40	Week 44	Week 48	Week 52	
Adverse events / SAE	D		X	Continuous																		
Biomarker Assessments		7.2.4																				
	D	7.2.4.1	X (Screening window - 56 days)												X							
	D	7.2.4.1	X (Screening window - 56 days)																			
Blood collection for Low level mutation analysis	D	7.2.4.2		X	Upon visit to confirm loss of MMR																	
	D	7.2.4.2		X																	X	
	D	7.2.4.2		X																		

Visit name	Category	Protocol Section 7	Screening Phase	Treatment Phase																	

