Visit name			EOT (Bosutinib) / S-Screening/ S-Baseline	S-Week 1 Day 1	S-Week 2 Day 1	S-Week 4	S-Week 6	S-Week 8	S-Week 10	S-Week 12	S-Week 14	S-Week 16	S-Week 20	S-Week 24	S-Week 28	S-Week 32	S-Week 36	S-Week 40	S-Week 44	S-Week 48	S-Week 52	
IRT																						
Treatment Switch Eligibility checklist	D		X																			
Treatment switch criteria	D		X																			
Mutation status	D	7.1.2.4	X																			
Prior/concomitant medications	D	7.1.2.4	X	Continuous																		
Physical examination	S	7.2.2.1	X	X		X	If needed	X	If needed	X	If needed	X	X	X	X	X	X	X	X	X	X	X
Extramedullary Involvement	D	7.2.2.1	X	X		X	If needed	X	If needed	X	If needed	X	X	X	X	X	X	X	X	X	X	X
ECOG Performance status	D	7.2.2.4	X	X		X	If needed	X	If needed	X	If needed	X	X	X	X	X	X	X	X	X	X	X
Weight	D	7.2.2.3	X	X						X				X			X			X		
Vital signs	D	7.2.2.2	X	X	X	X	If needed	X	If needed	X	If needed	X	X	X	X	X	X	X	X	X	X	X
Laboratory assessments		7.2.2.5																				

Visit name	Category	Protocol Section 7	Switch Screening Phase	Treatment Switch Phase																	
				S-Week 1 Day 1	S-Week 2 Day 1	S-Week 4	S-Week 6	S-Week 8	S-Week 10	S-Week 12	S-Week 14	S-Week 16	S-Week 20	S-Week 24	S-Week 28	S-Week 32	S-Week 36	S-Week 40	S-Week 44	S-Week 48	S-Week 52
Hematology	D	7.2.2.5.1	X (if not done at EOT)	X	X	X	X	X	X	X	X	X	X	X	X	X	X	X	X	X	X
Chemistry	D	7.2.2.5.2	X (if not done at EOT)	X	X	X		X		X		X	X	X	X	X	X	X	X	X	X
Chemistry-Hemoglobin A1c	D	7.2.2.5.2	X (if not done at EOT)	Week 12 and as clinically indicated																	
Coagulation	D	7.2.2.5.2	X (if not done at EOT)	X	X	X		X		X		X	X	X	X	X	X	X	X	X	X
Serum Pregnancy test (if applicable)	D	7.2.2.5.3	X (if not done at EOT)			X		X		X		X	X	X	X	X	X	X	X	X	X
Liver assessments	D			as clinically indicated																	

Visit name	Category	Protocol Section 7	Switch Screening Phase	Treatment Switch Phase																	
				S-Week 1 Day 1	S-Week 2 Day 1	S-Week 4	S-Week 6	S-Week 8	S-Week 10	S-Week 12	S-Week 14	S-Week 16	S-Week 20	S-Week 24	S-Week 28	S-Week 32	S-Week 36	S-Week 40	S-Week 44	S-Week 48	S-Week 52
Efficacy assessments		7.2.1																			
Blood collection for BCR-ABL1 quantification by RQ-PCR	D	7.2.1.1	X			X		X		X		X		X				X			X
Exploratory BCR-ABL1 Mutation analysis by Sanger sequencing	D	7.2.1.1		X (if not done at EOT)																	
Exploratory BCR-ABL1 Mutation analysis by Sanger sequencing for patients with mutations at Week 1 Day 1	D	7.2.1.1								X				X				X			X

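### Amendment 3 schedules no pregnancy test at the first dose or at the switch to asciminib: the latest result may be 21 days old at entry, and its age at the switch has no stated limit

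*Combined protocol and SAP*

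**What the plan says.** The current schedule is in the Amendment 3 protocol.

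- **Section 7.1.2.** The window is "All screening/baseline assessments (with the exception of Bone Marrow Aspirates) should occur within 21 days before Week 1 Day 1". The list of what must be done before the first dose begins with "Laboratory baseline assessments (including hematology, chemistry, coagulation and serum pregnancy test".
- **Table 7-1, serum pregnancy row.** Marked at Screening (Day -21 to -1), blank at Week 1 Day 1 and Week 2 Day 1, then marked at Weeks 4, 8, 12 and 16 and every four weeks to Week 96. Once visits become 12-weekly, urine tests are added monthly between them.
- **Table 7-2, switch phase.** One column serves as bosutinib end of treatment (EOT), switch screening and switch baseline. The pregnancy entry there is conditional on the test not having been done at EOT. S-Week 1 Day 1 and S-Week 2 Day 1 are blank, and the next mark is at S-Week 4.
- **Section 5.3.** Criterion 18 excludes pregnant women. Criterion 19a requires highly effective contraception during dosing, for 3 days after asciminib and for one month after bosutinib.
- **Section 1.2.1.1.** "Fetal malformations and increased visceral and skeletal variants were observed in the rat embryo-fetal development study". The rationale for Amendment 3 describes cardiac malformations in rats and, at low incidence, in rabbits.

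The written testing rule is available only in the Amendment 1 protocol. Under its Section 7.2.2.5.3, women of childbearing potential "have to complete a serum pregnancy test at the screening visit, at every monthly visit until end of treatment visit". Its Table 7-4 gives the frequency as "Screening/Baseline, every 4 weeks up to week 96, and every 12 weeks thereafter, EOT, unscheduled".

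**The concern.** Criterion 18 matters most when drug is first given. Under this schedule the evidence that it is met can be three weeks old at entry. At the switch it is as old as the time since bosutinib EOT. The schedule tests every four weeks through the main treatment period and adds urine tests to keep monthly spacing after Week 96. The widest interval in the main phase thus falls around first exposure to a drug with animal evidence of fetal harm.

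The women affected are those who conceive, or whose early pregnancy becomes detectable, between the last test and the first dose. Such a pregnancy would be exposed from the first dose and need not be found until Week 4. There is a lesser effect on the analysis. The Amendment 2 change log makes discontinuation mandatory in pregnancy, and Section 10.4.3 of the Amendment 1 protocol counts discontinuation before Week 24 as non-response. This is a patient-safety point, not a threat to the primary comparison.

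**Working it through.** The documents state no figure for this gap, so there is none to reproduce. The check is calendar arithmetic on the two tables.

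**Are the blanks real?** In both tables the hematology and chemistry rows are marked at the first-dose visit and at Week 2 Day 1, while the pregnancy row is empty there. The blanks are therefore not a fault of text extraction, and blood is already drawn at those visits.

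**Inputs**

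- Age of the screening result at Week 1 Day 1: 1 to 21 days (Section 7.1.2; Table 7-1 heading).
- First dose to Week 4: 28 days. This reading fits a Week 24 visit that serves a 24-week endpoint. If Week 4 meant Day 22, it would be 21 days.
- Visit window up to Week 16: ±1 day (Amendment 1, Section 7.1.5; the Amendment 3 text is not available).
- Routine interval: 28 days.

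**Main phase.** Gap = age of the result at first dose + days from first dose to Week 4.

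- Longest nominal gap: 21 + 28 = 49 days, which is 49 - 28 = 21 days beyond the routine interval.
- With the ±1 day window: 48 to 50 days.
- Screening on Day -1: 1 + 28 = 29 days.
- If Week 4 means Day 22: 21 + 21 = 42 days (41 to 43 with the window).

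**Switch.** Gap = days from the EOT test to S-Week 1 Day 1 + 28. The first term has no stated limit in the available text, so it is varied as an assumption:

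| EOT to S-Week 1 Day 1 (assumed) | Gap to S-Week 4 |
|---|---|
| 0 days | 28 days |
| 7 days | 35 days |
| 14 days | 42 days |
| 21 days | 49 days |
| 28 days | 56 days |

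**Effect of a current result at the first-dose visit.** The interval from there to Week 4 is 28 days (29 with the window), the same as the routine interval. What changes is the age of the result at first dose, which no longer reaches 21 days.

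**The case against.** The strongest reply is that the documents do not contradict themselves. The Amendment 1 rule ties testing to visits, namely screening and then each monthly visit, and Table 7-1 does exactly that. It sets no maximum number of days between tests and asks for none on Day 1. This stands. A reader might infer that the 49 days breach a stated interval, but monthly spacing is the pattern of the schedule and not a written ceiling. The rule is also quoted from an earlier version. The Amendment 3 text of Sections 7.1.2.2, 7.1.5 and 7.2.2.5.3 was not available and could contain a further requirement.

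Several other stronger readings also go too far:

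- **Dosing with no test at all.** Section 7.1.2 requires a serum test before the first dose. The issue is the age of the result.
- **A fixed 56-day gap at the switch.** This assumes 28 days between EOT and the first asciminib dose. The 28 days in the switch conditions limit how long certain toxicities may take to resolve; they do not cap that interval.
- **Four weeks of undetected exposure as a special defect.** Every routine four-weekly interval allows the same. A first-dose result addresses only what happened since the previous test.
- **Known human harm, or harm shown in both arms.** The malformations cited are in rats and rabbits given asciminib. No fetal data for bosutinib are relied on here.

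Existing safeguards also count. Contraception is an eligibility condition, oral contraception must have been stable for at least 3 months, and Table 7-4 of the Amendment 1 protocol provides for unscheduled tests. These lower the chance of a pregnancy at dosing. None of them shows that criterion 18 is met on the day, and unscheduled tests are optional.

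**Conclusion.** The point holds as a gap in the schedule that should be closed. Neither Amendment 3 table has a pregnancy test at the first-dose visit. At entry the result may be up to 21 days old, and the nominal gap between tests is up to about 49 days, or 29 at best, against 28 routinely. At the switch it is 28 days plus an interval for which no limit was found. The main-phase figure assumes screening on Day -21 and Week 4 at 28 days after Day 1; the switch figures depend on the assumed interval. The documents do not give the number of women of childbearing potential, so the number affected cannot be estimated. The conclusion is subject to the Amendment 3 sections not available for this review.

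**What to change.** First check the Amendment 3 text of Sections 7.1.2.2, 7.1.5 and 7.2.2.5.3 for a test requirement before dosing or a limit on the time from bosutinib EOT to S-Week 1 Day 1. If neither is there, reconcile the pregnancy rows of Tables 7-1 and 7-2, and Section 7.1.2, with the monthly spacing used elsewhere and with exclusion criterion 18, so that the first-dose and switch visits are each covered by a current result. The type of test and its exact timing are for the sponsor to set. The cost is one additional pregnancy test for women of childbearing potential at a visit that already takes place, and no analysis needs to change.
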